7.1.7 Safety Analysis

The first endpoint is to evaluate the toxicity of the proposed therapy. The first four months of therapy will be used as the time period in which toxicity will be evaluated and stopping rules for unacceptable toxicity will be implemented. Rules for stopping therapy will be based on rate of withdrawal due to significant toxicity (grade IV, non-hematological, non-metabolic and non-peripheral neuropathy). A true withdrawal rate within first 4 months of 15% will be considered excessive. Withdrawal rate will be assessed after every ten patients are treated. Enrollment will not be held though until the 10th patient enrolled becomes evaluable. Sufficient evidence will be taken for a lower limit to the corresponding one sided 80% confidence interval that exceeds 15%. Operationally observed rates that say regimen is too toxic would be 2/5, 3/10, 4/15, 5/20, 6/25 and 7/30. If the true probability of withdrawal from the study is 5%, the probability of deeming this regimen as too toxic after 15 or 30 patients have been treated is approximately .03 and .03, respectively. If the true probability of withdrawal is 10%, these probabilities are approximately .13 and .15, respectively. On the other hand, if the true probability of withdrawal is .30, then the probability of judging this regimen as too toxic after 15 or 30 patients is approximately .78 and .91, respectively.

With the semi-continuous monitoring of the withdrawal rate, the estimate of this rate, should the study run to completion, will be biased slightly downward. Without consideration of this bias, 30 patients will allow us 80% confidence that the estimated withdrawal rate will be within approximately .094 of the true rate under the assumption that the true rate is 20%. The incidence of second cancers will also be collected.

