Hypothesis of this phase II study is that ixazomib and lenalidomide as maintenance therapy after autologous PBSC transplant for Multiple Myeloma will be safe and tolerable and prolong the time to disease progression post transplant. The treatment regimen is alternating ixazomib with lenalidomide every two months until disease progression, intolerable toxicity or maximum of 24 months of therapy. The dose of ixazomib is 4.0 mg po on days 1, 8 and 15 per each 28-day cycle given for two consecutive months, followed by then lenalidomide 10 mg po daily for two consecutive months, then ixazomib for two months etc. Dose reduction for toxicity will be incorporated. If >30 days off initially planned next cycle of therapy, then patient will be taken off study. Toxicity will be graded per CTCAE version 4.0. The first four months of therapy will be used as the time period to evaluate end point of toxicity for stopping rules. Toxicity that meets stopping rules will be determined based on the number of patients that are withdrawn from study for significant toxicity (grade IV, non-hematological, non-metabolic, non-peripheral neuropathy) and the number of patients who stop therapy for toxicity and are withdrawn from study as they could not recover adequately and resume therapy by 30 days from the initial stopping of the study drugs. We shall consider the withdrawal rate to be excessive, and hence the therapy to be too toxic, if the true withdrawal rate from the study exceeds 15% in the first four months. An interim analysis at 15 treated patients will be conducted. If > 50% of patients are unable to receive > 50% of planned therapy in first 12 months of treatment, the study will be terminated due to lack of feasibility. Another endpoint is time to disease progression. Patients will be followed for initial response and for progression of disease, response criteria will be determined by International Myeloma working group criteria. In patients with chemo-refractory disease at the time of ASCT, the therapy will be felt to be promising if median time to progression is >9 months. If chemo-sensitive disease at time of ASCT, the therapy will be felt to be promising if median time to progression is >41 months based on CALGB 10014 lenalidomide maintenance study post ASCT. Cytogenetic information will be collected and initial response rates and outcome will be descriptively reported. Patients will be followed for overall survival. The incidence of secondary cancers will also be collected. If this study regimen is deemed to be potentially efficacious and is not regarded as too toxic per stopping rules outlined above and observed EFS rate are consistent with rates that match or exceed historical benchmarks, then a phase III trial to show efficacy rate of this regimen over single agent therapy will be designed.

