2. STUDY OBJECTIVES

2.1 Primary Objectives

- Evaluate the toxicity of the use of ixazomib and lenalidomide as maintenance therapy after autologous transplant

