3. STUDY ENDPOINTS

3.1 Primary Endpoints

Toxicity

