7.1.8 Interim Analysis

An interim analysis at 15 treated patients will be conducted to assess feasibility for maintenance therapy. If > 50% of patients are unable to receive > 50% of planned therapy in first 12 months of treatment, the study will be terminated due to lack of feasibility.

If this study regimen is deemed to be potentially efficacious and is not regarded as too toxic per stopping rules outlined above and observed EFS rate are consistent with rates that match or exceed historical benchmarks, then a phase III trial to show efficacy rate of this regimen over single agent therapy will be designed.

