6.1 Clinical Trials Experience

Specific Populations

Newly Diagnosed Multiple Myeloma:

Data were evaluated from 1613 patients in a large phase 3 study who received at least one dose of REVCLIMID with low dose dexamethasone (Rd) given for 2 different durations of time (i.e., until progressive disease [Arm Rd Continuous; N=532] or for up to eighteen 28-day cycles [72 weeks, Arm Rd18; N=540] or who received melphalan, prednisone and thalidomide (Arm MPT; N=541) for a maximum of twelve 42-day cycles (72 weeks). The median treatment duration in the Rd Continuous arm was 80.2 weeks (range 0.7 to 246.7) or 18.4 months (range 0.16 to 56.7).

In general, the most frequently reported adverse reactions were comparable in Arm Rd Continuous and Arm Rd18, and included diarrhea, anemia, constipation, peripheral edema, neutropenia, fatigue, back pain, nausea, asthenia, and insomnia. The most frequently reported Grade 3 or 4 reactions included neutropenia, anemia, thrombocytopenia, pneumonia, asthenia, fatigue, back pain, hypokalemia, rash, cataract, lymphopenia, dyspnea, DVT, hyperglycemia, and leukopenia. The highest frequency of infections occurred in Arm Rd Continuous (75%) compared to Arm MPT (56%). There were more grade 3 and 4 and serious adverse reactions of infection in Arm Rd Continuous than either Arm MPT or Rd18.

In the Rd Continuous arm, the most common adverse reactions leading to dose interruption of REVCLIMID were infection events (28.8%); overall, the median time to the first dose interruption of REVCLIMID was 7 weeks. The most common adverse reactions leading to dose reduction of REVCLIMID in the Rd Continuous arm were hematologic events (10.7%); overall, the median time to the first dose reduction of REVCLIMID was 16 weeks. In the Rd Continuous arm, the most common adverse reactions leading to discontinuation of REVCLIMID were infection events (3.4%).

In both Rd arms, the frequencies of onset of adverse reactions were generally highest in the first 6 months of treatment and then the frequencies decreased over time or remained stable throughout treatment, except for cataracts. The frequency of onset of cataracts increased over time with 0.7% during the first 6 months and up to 9.6% by the 2nd year of treatment with Rd Continuous.

**Fred Hutchinson Cancer Research Center
Clinical Study Protocol [FHCRC 9266]**

Table 4 summarizes the adverse reactions reported for the Rd Continuous, Rd18, and MPT treatment arms.

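### No toxicity estimate is stated beyond month four, and the phase III toxicity condition rests on the four-month rule alone, although maintenance runs for up to 24 cycles

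*Combined protocol and SAP*

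**What the plan says.** The primary objective (Section 2.1) is: "Evaluate the toxicity of the use of ixazomib and lenalidomide as maintenance therapy after autologous transplant". Section 3.1 names the primary endpoint as toxicity, with no time window, grade or summary measure. Section 4.1 allows up to 24 cycles of 28 days.

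Section 7.1.7 opens with "The first endpoint is to evaluate the toxicity of the proposed therapy" and continues: "The first four months of therapy will be used as the time period in which toxicity will be evaluated" (the same sentence goes on to place the stopping rules in that period). It sets 15% withdrawal within four months as excessive, lists the stopping boundaries, and gives operating characteristics and a precision statement for that rate. Its only item beyond month four is that second cancers will be collected.

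The Protocol Summary words the window differently: "The first four months of therapy will be used as the time period to evaluate end point of toxicity for stopping rules". In Section 7.1.8, the toxicity condition for going on to phase III is that the regimen "is not regarded as too toxic per stopping rules outlined above".

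Collection goes further than analysis. The study flow chart has adverse events reviewed before dosing in cycles 5-24, and Section 6.15 has the primary reason for each withdrawal recorded.

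**The concern.** The trial asks whether an alternating regimen is tolerable as long-term maintenance. Read as written, Section 7.1.7 answers from the first four months, and 7.1.8 carries that answer into the phase III decision. Under the dispensing schedule, those months hold one block of each drug: 2 of 12 ixazomib cycles and 2 of 12 lenalidomide cycles. A patient who completes the first alternation and is withdrawn for toxicity in cycle 5 or later counts as a success in the only toxicity estimate the plan describes. The trial could then report the regimen as not too toxic on about a sixth of the planned course, without a prespecified figure for the rest.

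**Working it through.** **Inputs from the protocol.** Boundaries 2/5, 3/10, 4/15, 5/20, 6/25 and 7/30; n = 30; limit 15% within four months; one-sided 80% lower confidence limit (all 7.1.7). Up to 24 cycles of 28 days (4.1). Progression medians of 41 months (chemo-sensitive) and 9 months (chemo-refractory), which 7.1.6 gives as thresholds for a promising result, not as expected values.

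**1. The plan's own figures.** An exact sequential binomial calculation with looks after every 5 patients gives these probabilities of declaring the regimen too toxic:

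| True four-month rate | After 15 | After 30 | Plan states |
|---|---|---|---|
| 5% | .030 | .031 | .03 / .03 |
| 10% | .129 | .146 | .13 / .15 |
| 30% | .775 | .912 | .78 / .91 |

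The precision figure also reproduces: 1.2816 × √(0.2 × 0.8/30) = .0936, against .094 stated. All of these describe the four-month withdrawal rate. The chance of passing the rule is 1 − .146 = .854 at 10% and 1 − .031 = .969 at 5%. With looks every 10 patients, as the text of 7.1.7 says, the chances are .904 and .987.

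**2. Share of the course.** 4/24 = 16.7% if a month is taken as a cycle. Four calendar months are 4 × 30.44/28 = 4.35 cycles, or 18.1% of 24.

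**3. What a four-month rate could mean over 24 cycles.** This step rests on assumptions that are not in the protocol.

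- Course length: T = 24 × 28/30.44 = 22.08 months.
- Toxicity-withdrawal hazard: h = −ln(1 − q)/4, which is .02634 per month for q = 10% and .01282 for q = 5%.
- Progression hazard: g = ln 2/median, which is .01691 for 41 months and .07702 for 9 months.
- Cumulative incidence: h/(h + g) × [1 − exp(−(h + g)T)].

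(a) Constant hazard, 41-month median:
- q = 10%: .6091 × (1 − .3849) = .375
- q = 5%: .4313 × (1 − .5187) = .208

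(b) Hazard halved after month 6, 41-month median. The first six months and the remaining 16.08 are added:
- q = 10%: .6091 × (1 − .7715) + .7715 × .4379 × (1 − .6166) = .139 + .130 = .269
- q = 5%: .4313 × (1 − .8366) + .8366 × .2750 × (1 − .6874) = .070 + .072 = .142

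(c) Constant hazard, 9-month median:
- q = 10%: .2548 × (1 − .1021) = .229
- q = 5%: .1427 × (1 − .1376) = .123

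The range is thus about 23% to 37% for a four-month rate of 10%, and about 12% to 21% for 5%. It takes each departure from (a) singly. Both together would give .2548 × (1 − .5379) + .5379 × .1460 × (1 − .2346) = .178 and .1427 × (1 − .5833) + .5833 × .0769 × (1 − .2615) = .093. Toxicity that accumulates would push the figures above (a).

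**4. Choice of estimator.** In case (a) at 10%, one minus Kaplan-Meier, with progression censored, gives 1 − exp(−.02634 × 22.08) = .441 against .375. A full-course estimate should therefore treat progression as a competing event.

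**The case against.** Several stronger readings are tempting, and the protocol does not support them.

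- **Late toxicity withdrawals affect no decision at all.** A reader might infer this, but the feasibility rule in 7.1.8 ends the study if more than half of patients cannot receive more than half of planned therapy in the first 12 months. A withdrawal in months 5-6, or long holds up to month 12, can count there. The rule measures therapy delivered, whatever the cause, is tied to an interim look at 15 patients, and covers nothing after month 12. It does not replace a toxicity estimate.
- **The Summary and 7.1.7 contradict each other.** Both sentences join the toxicity endpoint to the stopping rules, and the Summary does not say that the window serves those rules exclusively. Section 7.1.7 can be read as describing the stopping window alone. That reading leaves the primary endpoint with no stated analysis for cycles 5-24, so the gap remains.
- **Late toxicity is ignored.** It is not. Adverse events are reviewed throughout treatment, and Section 8.2 requires new primary malignancies to be reported for at least three years after the last dose. The gap is in the analysis.
- **The appended package insert shows toxicity building up.** For lenalidomide with dexamethasone it says: "In both Rd arms, the frequencies of onset of adverse reactions were generally highest in the first 6 months of treatment". The same sentence goes on to say that frequencies then fell or stayed stable, except for cataracts. That regimen also differs in dose, partner drug and population. The insert supports a falling or stable hazard at least as well as accumulation.

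Four months also covers one full alternation of both drugs and is a defensible window for stopping and early tolerability. Replacing the primary endpoint with a 24-cycle measure would be a design choice that the gap does not force.

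**Conclusion.** The point holds as a cheap improvement. Section 7 gives no toxicity estimate beyond month four, and the phase III toxicity condition cites the four-month rule alone, while the objective concerns maintenance for up to 24 cycles. That much follows from the text and needs no modelling. The illustrative range in the working rests on an assumed hazard shape and on borrowed progression medians, so it shows the possible scale and does not predict this regimen's rate. It does show that passing the four-month rule is compatible with very different full-course results.

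**What to change.** Keep the four-month withdrawal rate and its boundaries as the stopping rule and early tolerability measure. Then:

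- In 7.1.7, state that toxicity is evaluated over all treatment cycles and that the four-month window applies to the stopping rule. Add the cumulative incidence of toxicity withdrawal through cycle 24, with a confidence interval and with progression, non-toxic withdrawal and non-toxic death as competing events. Add a worst-grade toxicity table over all cycles.
- In 7.1.8, have the phase III decision consider this full-course estimate alongside the stopping rule.
- Align the Summary with the new wording.

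The cost is wording and slightly more analysis of data already collected; no visit or treatment rule changes. Section 4.3 follows the last patient for two years from the start of treatment, and 24 cycles take 22.1 months before any delays.

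The full-course figure will come later and look less favourable than the four-month one, and at n = 30 it will be imprecise: at 37% the binomial standard error is √(.37 × .63/30) = .088. No acceptable 24-cycle rate has been set, so the estimate would inform the phase III decision without a pass mark unless the investigators choose one.

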6.4 Dose-Modification Guidelines

6.4.1 Recommended Ixazomib Criteria for Beginning or Delaying a Subsequent Treatment Cycle & Dose Modifications for Treatment Associated Toxicity

Treatment with ixazomib will use a cycle length of 28 days. For a new cycle of treatment to begin, the patient must meet the following criteria:

- ANC must be $\geq 1,000/\text{mm}^3$.
- Platelet count must be $\geq 75,000/\text{mm}^3$.
- All other nonhematologic toxicity (except for alopecia) and peripheral neuropathy must have resolved to \leq Grade 1 or to the patient's baseline condition.

If the patient fails to meet the above-cited criteria for initiation of the next cycle of treatment, dosing should be delayed for 1 week. At the end of that time, the patient should be re-evaluated to determine whether the criteria have been met. If the patient continues to fail to meet the above-cited criteria, delay therapy and continue to reevaluate. The maximum delay before treatment should be discontinued will be 30 days or at the discretion of the Principal Investigator.

For dosing recommendations upon recovery, refer to Table 6-1, Table 6-2, and Table 6-3.

**Fred Hutchinson Cancer Research Center
Clinical Study Protocol [FHCRC 9266]**

Table 6-1 Ixazomib Dose Adjustments

Dose Level	Dose (mg)
Starting Dose	4.0 mg
-1	3.0 mg
-2	2.3 mg
-3	Discontinue

Dosing adjustments for hematologic toxicity are outlined in Table 6-2.

Table 6-2 Ixazomib Dose Adjustments for Toxicities

Criteria	Action
Within-Cycle Dose Modifications	
• If platelet count $\leq 30 \times 10^9/L$ or ANC $\leq 0.50 \times 10^9/L$ on a ixazomib dosing day (other than Day 1)	
• Ixazomib dose should be withheld.• Complete blood count (CBC) with differential should be repeated at least every other day until the ANC and/or platelet counts have exceeded the prespecified values (see Section 6.4.1) on at least 2 occasions.• Upon recovery, ixazomib may be reinitiated with 1 dose level reduction.
Dose Modifications for Subsequent Treatment Cycles	

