6.15 Termination of Treatment and/or Study Participation

Patients will be informed that they have the right to withdraw from the study at any time for any reason, without prejudice to their medical care. The investigator also has the right to withdraw patients from the study for any of the following reasons:

- Adverse event
- Protocol violation
- Lost to follow-up
- Progressive disease
- Study terminated
- The treatment appears detrimental in the judgment of primary physician

**Fred Hutchinson Cancer Research Center
Clinical Study Protocol [FHCRC 9266]**

- They develop non-hematological, non-metabolic, non-peripheral neuropathy grade IV toxicity
- They are unable to resume therapy more than 30 days after initial stopping of therapy for toxicity or cannot tolerate lowest dose reduction level
- Repeated noncompliance to protocol in view of principal investigator

Patients who are withdrawn from the study will not be replaced.

At the time of withdrawal, all study procedures outlined for the End of Study visit should be completed per study calendar (See Study Flow Chart). The primary reason for patient's withdrawal from the study should be recorded in the source documents and CRF.

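### The toxicity stopping rule is defined by two different withdrawal counts; Section 7.1.7 omits the 30-day non-recovery withdrawals that the Protocol Summary includes, which makes passing more likely

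*Combined protocol and SAP*

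**What the plan says.** The Protocol Summary (Overview of Study Design) builds the stopping rule from two counts:

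- (a) withdrawals for grade IV toxicity other than hematological, metabolic or peripheral neuropathy;
- (b) a second group, described as "patients who stop therapy for toxicity and are withdrawn from study as they could not recover adequately and resume therapy by 30 days".

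It calls the regimen too toxic "if the true withdrawal rate from the study exceeds 15% in the first four months".

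Section 7.1.7 gives the boundaries (2/5, 3/10, 4/15, 5/20, 6/25, 7/30) and the stopping probabilities. It names only (a): "Rules for stopping therapy will be based on rate of withdrawal due to significant toxicity (grade IV, non-hematological, non-metabolic and non-peripheral neuropathy". It then sets the same limit over the same window: "A true withdrawal rate within first 4 months of 15% will be considered excessive". Its later sentences speak of withdrawal without qualification.

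Section 6.15 lists the two as separate reasons for withdrawal. One is "They develop non-hematological, non-metabolic, non-peripheral neuropathy grade IV toxicity"; the other is "They are unable to resume therapy more than 30 days after initial stopping of therapy for toxicity or cannot tolerate lowest dose reduction level".

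**The concern.** One limit and one set of boundaries are attached to two different rates. The difference has content. Under Section 6.4.1, low neutrophil or platelet counts and unresolved neuropathy hold the next ixazomib cycle ("If the patient continues to fail to meet the above-cited criteria, delay therapy and continue to reevaluate"), and Section 6.4.2 sets the same kind of entry criteria for lenalidomide. Both kinds of toxicity are excluded from (a), so a withdrawal for either can count only through (b). The same holds for lower-grade toxicity that does not resolve.

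Toxicity is the only primary endpoint (Section 3.1), and Section 7.1.8 makes passing this rule a condition for designing the phase III trial. The same data can give opposite verdicts. Suppose there are three toxicity withdrawals in the first ten patients, two of type (a) and one of type (b). The Summary's count is 3/10, which is too toxic. The 7.1.7 count is 2/10, and the trial continues. (With looks every five, this holds unless both type (a) cases fall in the first five patients, where 2/5 stops the trial on either count.)

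**Working it through.** **Inputs.** Boundaries, 15% limit and quoted probabilities: Section 7.1.7. Sample size 30: Section 4.2. The share of toxicity withdrawals that are type (a) is not in the documents, so it is an assumption, run from 100% to 25%.

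**Method.** Exact binomial recursion: stop at the first look where the withdrawal count reaches the boundary. Section 7.1.7 describes assessment after every ten patients but lists boundaries every five, so both schedules are shown; that discrepancy is a separate point.

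**Reproducing the plan's figures.** Looks every five, chance of stopping by 15 / by 30 patients:

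| True rate | Plan | Recomputed |
|---|---|---|
| 5% | .03 / .03 | .030 / .031 |
| 10% | .13 / .15 | .129 / .146 |
| 30% | .78 / .91 | .775 / .912 |

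These probabilities depend only on the rate entered, so they do not show which count was intended.

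**Direction.** Every type (a) withdrawal is also in the Summary's count. With the same boundaries, the 7.1.7 count can never stop the trial when the Summary's count would not. This needs no assumption about the share.

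**Size.** Counted rate under 7.1.7 = true rate (Summary definition) × type (a) share. For example, 30% × 50% = 15%. Chance of stopping by 30 patients:

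| True rate | Share (a) | Counted rate | Looks every 5 | Looks every 10 |
|---|---|---|---|---|
| 30% | 100% | 30% | .912 | .892 |
| 30% | 90% | 27% | .848 | .817 |
| 30% | 75% | 22.5% | .701 | .650 |
| 30% | 50% | 15% | .354 | .285 |
| 30% | 25% | 7.5% | .076 | .042 |
| 20% | 100% | 20% | .594 | .532 |
| 20% | 90% | 18% | .499 | .432 |
| 20% | 75% | 15% | .354 | .285 |
| 20% | 50% | 10% | .146 | .096 |
| 20% | 25% | 5% | .031 | .013 |

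At a true 30%, the chance of stopping falls to .80 at a share of 84% (every five) or 88% (every ten), and to .50 at 60% or 64%.

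**Opposite verdicts.** Because one count contains the other, the chance that the two wordings disagree is the difference between the two stopping probabilities. At a true 20% with looks every five, it is .594 − .354 = .240 at a 75% share and .594 − .146 = .447 at 50%. With looks every ten, it is .532 − .285 = .247 and .532 − .096 = .436.

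**Backstop.** The feasibility check in Section 7.1.8 needs more than half of 15 patients to fail, so at least 8. If early toxicity withdrawals were the only failures, P(X ≥ 8 of 15) is .050 at a true 30% and .004 at 20%.

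**The case against.** The strongest reply is that 7.1.7 merely abbreviates the Summary. The grade IV wording appears in one sentence, and the rest of the section speaks of withdrawal in general, with the same 15% and four months. That reading is available but unproven. The wording in 7.1.7 repeats the definition the Summary gives to component (a) alone, and (b) is never mentioned in the section an analyst would apply.

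Second, the effect is assumed, not known. This stands: at a 90% share the loss at a true 30% is only .912 − .848 = .064, and nothing in the documents supports 50% or 25% in particular. Equally, nothing supports 100%, the only share at which the loss vanishes.

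Third, evidence that (b) will occur is thin. In the lenalidomide label's MDS study (10 mg), first interruptions for adverse events lasted a median of 22 days, range 2–265. That is another disease, and these are interruptions rather than withdrawals. It shows only that (b) need not be empty. Timing also limits (b) on lenalidomide: cycle 3 starts on day 2 × 28 + 1 = 57, and a 30-day non-recovery completes within four 28-day cycles (112 days) only if dosing stopped by about day 112 − 30 = 82. Most stops in cycle 4, which starts on day 85, would complete later. This does not limit (b) during the first ixazomib cycles.

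Fourth, the feasibility figure is a lower bound, since progression and later withdrawals may also count as failures. That check still does not replace the toxicity rule.

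**Conclusion.** The conflict is real and should be resolved before the rule is applied. That 7.1.7 is the more lenient version relative to the Summary is certain; by how much is not. At a true 30%, the chance of stopping (looks every five) falls from .91 to between .85 and .08 as the assumed grade IV share goes from 90% to 25%. At a true 20% it falls from .59 to between .50 and .03. A regimen above the 15% limit can pass under either count; even with full counting, a true 20% passes 1 − .594 = 41% of the time. What the wording changes is how often. Because the count decides the primary endpoint's verdict and can reverse it on the same data, this must be fixed.

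**What to change.** State the Summary's two-part toxicity-withdrawal count in Section 7.1.7, and say that the 15% limit, the boundaries and the quoted probabilities all refer to that one rate. The Summary itself ties the 15% to the two-part count, so none of those figures needs to change. In the same sentence, say whether withdrawal because the lowest dose level is not tolerated (Section 6.15) counts, and whether the stopping date or the withdrawal date must fall within the four months. If the sponsor in fact meant the narrower rate, the Summary must be changed instead.

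The cost is small. Section 6.15 already requires that the primary reason for a patient's "withdrawal from the study should be recorded in the source documents and CRF". The rule will trigger more often than under the narrow count, including for acceptable regimens: at a true 10% and an even split, .15 instead of .03 (looks every five) or .10 instead of .01 (every ten). Section 7.1.7 already quotes about .15 for a true 10%. Some patients will be classified up to 30 days later.

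The documents also differ on when the 30 days start and on whether going off study is mandatory or discretionary (Summary; Sections 4.1, 6.1, 6.4 and 6.15). Those passages need to be reconciled separately; no view is taken here on which clinical rule is right.
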